3.2.3. REMOVAL OF SUBJECTS FROM THERAPY OR ASSESSMENT

3.2.3.1. CRITERIA FOR WITHDRAWAL OF SUBJECTS FROM STUDY

Participation in the study is strictly voluntary. A subject has the right to withdraw from the study at any time, for any reason.

Subjects who terminate study participation for reasons of lost to follow-up, informed consent withdrawal, or death will not have any follow-up assessments.

In the event a subject is discontinued from the study, the study monitor and the Sponsor will be informed immediately.

3.2.3.2. SUBJECT DISCONTINUATION CRITERIA

The subject discontinuation criteria are described below:

Efficacy discontinuation criteria:

Any subject with < 20% improvement from baseline (of the respective initial Phase IIb study) in both swollen and tender joint count (SJC and TJC; 66/68 counts) at any of the visits at Week 12, 24, 36, 48, 60, 72, 84 or 96, will discontinue from the trial. The visit at which subjects will meet the efficacy discontinuation criteria, is defined as the Early Termination Visit for these patients. Subjects who have to discontinue study drug but are not withdrawing consent for post-treatment follow-up, should return for the Follow-up Visit, planned 12 weeks after the last study drug administration, according to section 3.4.1.3.

Study drug must also be permanently discontinued if any of the following occurs:

- Serious hypersensitivity reaction.
- Following abnormalities in laboratory test results: ALT and/or AST elevations between > 3 and \leq 5 x ULN (confirmed by repeat testing within 2-4 weeks), ALT or AST elevations > 5 x ULN, absolute neutrophil count < 1×10^9 /L, or a platelet count < 50×10^3 / μ L.
- Diagnosis of or suspicion of a serious infection (requiring parenteral antibiotics and/or hospitalization) or TB.
- Malignancy.
- Pregnancy or pregnancy planned within the study period

- Demyelinating disease.
- The initiation of protocol-prohibited medications (see section [3.3.5](#)).
- CHF class III or IV as defined by the New York Heart Association, unstable angina pectoris, myocardial infarction, cerebrovascular accident.
- In case of interruption of study drug administration for 2 consecutive doses.
- The Investigator or the Sponsor's medical monitor deems it is in the subject's best interest.

Discontinuation of study drug must be considered for subjects who develop a severe study drug injection-site reaction or a severe hypersensitivity reaction.

Subjects who have to discontinue according to these criteria but are not withdrawing consent for post-treatment follow-up should return for the Early Termination Visit planned 2 weeks after the last study drug administration (unless they discontinue during a study visit, in which case that becomes their Early Termination Visit). Subjects should also have a Follow-up Visit planned 12 weeks after the last study drug administration, according to section [3.4.1.3](#).

A description of procedures to be performed for subjects who withdraw from the study or study drug will be provided in section [3.4.1.3](#) (also see Early Termination Visit in the [Schedule of Assessments](#)).

For all subjects, every effort should be made to contact the medical monitor prior to discontinuing study drug, where medically feasible. If there is a medical reason for discontinuation, the subject will remain under the supervision of the Investigator until satisfactory health has returned unless the subject withdraws his consent and is no longer willing to come to the visits. Subjects who discontinue will not be replaced.

3.2.3.3. STUDY TERMINATION

If the Sponsor abandons the study prior to commencement of any protocol activities, and after IEC/IRB and Competent Authority (CA) approvals have been received, the Investigator or Sponsor must notify the IEC/IRB and CA by letter outlining the reasons for abandonment of the study.

At any time during the study, the Sponsor may suspend or terminate the study or part of the study for any reason. If the Investigator suspends or terminates participation in the study, the Investigator will promptly inform the Sponsor and the IEC/IRB and provide them with a detailed written explanation. The Investigator will also return all study drug, study drug containers, and other study materials to the Sponsor or its designee.

Upon study completion, the Sponsor will provide the Investigator, IEC/IRB, and CA with final reports and summaries as required by regulations.

In case of suspension or halt due to safety reasons, the CA and IEC/IRB will be notified immediately and at the latest within 15 days after the study is halted, clearly explaining the reasons, and describe follow-up measures, if any, taken for safety reasons.

3.3. TREATMENT OF SUBJECTS

For an overview of the treatments to be administered, please refer to section [3.1](#).

3.3.1. IDENTITY OF STUDY DRUG

- Study drug:
 - Active substance: ALX-0061 Nanobody.
 - Activity: ALX-0061 Nanobody binds to the IL-6R and inhibits the interaction between the IL-6 ligand and the receptor subunit, thereby preventing receptor signaling.
 - Pharmaceutical formulation: ALX-0061 Drug Product is a clear, yellow to brown-yellow solution in an aqueous medium with a nominal concentration of 150 mg/mL of ALX-0061 and containing the following excipients: L-histidine, L-histidine hydrochloride monohydrate, polysorbate 80 (Tween 80), sucrose, and water for injections. ALX-0061 will be supplied as a sterile liquid for s.c. injection at a volume of 1.0 mL in pre-filled single-use syringes. No preservatives are present.
 - Route and volume of administration: s.c. injections at a volume of 1.0 mL.

The Sponsor will be providing adequate supplies of ALX-0061 for this study.

3.3.2. DRUG ACCOUNTABILITY

The Pharmacist or his/her designee is responsible for acknowledge receipt of each shipment of study drug and will verify the condition and quantity.

The study drug will be kept in a locked and secured storage facility accessible only to those authorized by the Investigator to dispense the study drug.

The responsible person will keep an inventory. This will include a description of the formulation and the quantity of study drug received for the study and a record of the materials that are dispensed, to whom and when.

At all time points when the subjects are to self-administer the study drug, the subject will note the exact timing of dosing in the study drug injection card. At every next visit, subjects are required to return all study drug supplies (used and unused syringes) to study sites.

On termination of the study, the pharmacist, the Investigator and/or designated personnel will conduct a final inventory of the study drug supply and will record the results of this inventory on the Drug Accountability Form. All study drug supplies

will be returned to and destroyed by a vendor upon Sponsor approval, or will be locally destroyed according to site procedure upon Sponsor approval.

Instructions for study drug accountability are available in the Study Drug Manual.

3.3.3. STUDY DRUG HANDLING

Instructions for study drug administration, handling, and storage, are available in the Study Drug Manual.

Packaging and Labeling

The study drug will be labeled in accordance with local regulations. Each label will contain, but will not be limited to, study number, storage conditions, dosing instructions, Sponsor's name, address, and telephone number.

One kit will contain 1 syringe.

Storage

Study drug will be provided under refrigerated conditions and must be stored in a secure, limited-access location under the storage conditions specified by the Sponsor.

ALX-0061 must be refrigerated at 2°C to 8°C (35.6 °F to 46.4 °F) and should be stored in the secondary packaging until administration. It should not be frozen or shaken.

Site storage conditions should be monitored by the site personnel and reviewed by the monitor during site visits. Deviations from the storage requirements must be documented and reported to the Sponsor, according to the instructions provided in the Study Drug Manual.

Verbal and written instructions for proper storage, handling, and administration of the study drug will be given to the subject, and will include instructions to contact the study site immediately if they experience problems with the study drug and/or administration.

Dispensing

The Investigator or qualified designee(s) will dispense study drug to subjects who have met the entry criteria. Clinical supplies may not be used for any purpose other than that which is stated in this protocol.

See the [Schedule of Assessments](#) for when clinical supplies are to be dispensed to the subjects. For self-injections, enough study drug until the next visit will be provided for the subjects to take home. All used and unused syringes should be returned to the site at the following clinic visit. At each visit, the site will review the

injection card to check whether the pre-filled syringes were used, partially used, or unused by the subject.

Product Quality Complaint

Any malfunctioning pre-filled syringe has to be communicated (written or electronically) and returned to the Sponsor or its designee upon Sponsor's request.

3.3.4. STUDY DRUG INJECTIONS

At the study visits at Weeks 0, 4, 8, 12, 24, 36, 48, 60, 72, 84 and 96, study drug is to be administered s.c. at the study site. Subjects will remain at the site for 60 minutes after the injection in order to assess adverse reactions.

At all other time points, subjects are allowed to self-administer away from the clinic (after proper training in s.c. injection technique at Week 0). Subjects unable to have injections administered away from the study site will be required to return to the site every 2 weeks for administration of study drug by an authorized health professional.

All subjects are to receive 1 injection in the abdominal region at each dosing day. As injections are to be performed q2w, all injections can be performed in an abdominal quadrant of choice. However, note that the area of administration needs to be evaluable for local skin reaction (normal skin without skin burns, scars, or large tattoos in the area of administration). The abdominal quadrants used for the administrations will be recorded in the (electronic) Case Report Forms ([e]CRFs).

Detailed instructions for study drug administration are available in the Study Drug Manual.

No constraints with regard to timing of study drug administration during the day of dosing are to be taken into account. The exact times of medication dosing at the clinical site will be recorded in the (e)CRF.

3.3.5. PRIOR AND CONCOMITANT THERAPY

Prior and concomitant medication are documented throughout the study.

During the 104-week treatment and assessment period of the study, subjects are not allowed to initiate DMARDs (other than MTX for subjects who completed the preceding Study ALX0061-C201, see below).

Permitted Medication

Subjects who completed the prior combination therapy study (Study ALX0061-C201) will receive ALX-0061 and will be recommended to continue

with MTX, while subjects who completed the prior monotherapy study (Study ALX0061-C202; except those who were assigned to TCZ) will receive ALX-0061 as monotherapy.

MTX will not be considered one of the study agents and the MTX dose can be adjusted at the Investigator's discretion.

Commercially available MTX will be used in this study and will not be provided by the Sponsor. Continued supplementation with oral folic acid or oral folinic acid should be given at the discretion of the treating physician for patients on MTX.

Subjects treated with NSAIDs (including aspirin and selective cyclooxygenase 2 inhibitors) and other analgesics (except high-potency opioid analgesics; see prohibited medication) should receive the usual marketed doses approved in the country in which the study is being conducted, and should be on a stable dose whenever possible until the Week 104 visit, or until the Early Termination Visit. Changes in the dose may be done at the discretion of the Investigator if he/she feels it is medically justified. Whenever possible, short-acting NSAIDs and other analgesics should not be administered within 6 hours before study assessments. Long-acting ones can be maintained at their usual dosing intervals before study assessments.

Subjects treated with oral corticosteroids should receive a stable dose equivalent to ≤ 10 mg of prednisone/day, up to and including Week 104, or until the Early Termination Visit. The dose of oral corticosteroid may be changed at the discretion of the Investigator.

The number of intra-articular (i.a.) corticosteroid injections is limited to 2 injections over a 104-week period. The joint(s) affected by the procedure(s) will be considered as swollen and tender for 28 days/4 weeks in the data analyses from the date of the procedure onward.

The use of concomitant medication will be evaluated at Weeks 0, 4, 8, and 12, and every 12 weeks thereafter; however, treating physicians should monitor MTX and other therapies in accordance with appropriate clinical guidelines.

The expression of hepatic CYP450 enzymes is suppressed by IL-6. IL-6 blocking might therefore influence (normalize) CYP450 expression and products that are substrates for CYP450 enzymes (e.g., statins, warfarin, theophylline, oral contraceptives, calcium antagonists phenytoin, cyclosporine, benzodiazepines) could be metabolized faster. Subjects taking medicinal products which are metabolized via CYP450 3A4, should be closely monitored and their treatment might have to be adapted if necessary in order to maintain therapeutic efficacy. Subjects on warfarin will be monitored by assessment of INR (see [Schedule of Assessments](#)); the lipid levels will be evaluated which will be of help to monitor the

subjects on statins (see [Schedule of Assessments](#)). If needed, the Investigator or the relevant treating physician should adapt the treatment of the concerned subject (unscheduled visits can be planned upon the discretion of the treating physician). Given the long half-life of ALX-0061, the influence on the hepatic enzymes can persist for several weeks.

Other medication (e.g., to treat AEs) may only be prescribed after consultation with the Investigator, unless in case of an emergency situation that does not allow discussion.

Prohibited Medication

The following medications are prohibited during the study (up to and including Week 104 or Early Termination Visit):

- DMARDs (other than MTX for subjects who completed the preceding Study ALX0061-C201).
- Intramuscular (i.m.) administration of corticosteroids for the treatment of RA. In this study, oral corticosteroids can be increased to 10 mg/day. For i.a. dosing see "permitted medication".
- High-potency opioid analgesics, including but not limited to hydrocodone, metopon, oxycodone, clonitazene, hydromorphone, oxymorphone, morphine, fentanyl, levorphanol, buprenorphine, methadone, meperidine.
- Use of, any biological DMARD, targeted synthetic DMARD (such as tofacitinib), or investigational drugs.
- Use of any live attenuated vaccine.

Contraceptives

Female subjects of childbearing potential (excluding postmenopausal women, sterilized, ovariectomized, and hysterectomized women) must agree to use 2 generally accepted adequate contraceptive methods of which 1 is a barrier method (e.g., hormonal contraception stabilized for at least 1 month [oral, patch, depot, injectable, vaginal ring] in combination with condom by partner) or should agree upon continuous abstinence from heterosexual contact from screening/baseline until at least 6 months after last dosing.

No additional contraceptive method is needed in case of surgical sterilization (at least 3 months prior to screening/baseline), hysterectomy, a partner who has been vasectomized (at least 3 months prior to screening/baseline).

Male subjects should use condoms for the duration of the study and for at least 6 months after last administration of study drug.

Other

During the study, no alcohol abuse or drug abuse is allowed.

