1.2.4.1. STUDY ALX-0061-1.1/10 IN SUBJECTS WITH MODERATELY TO SEVERELY ACTIVE RHEUMATOID ARTHRITIS

The results of the SAD and MAD parts of this study are discussed in detail in the Investigator's Brochure and are briefly summarized below.

Efficacy in the MAD Part

In the MAD part of the study, all ALX-0061 treatment combinations showed rapid and long-lasting improvements in disease activity (as measured by ACR, EULAR, Disease Activity Score using 28 joint counts (DAS28) [CRP], Clinical Disease Activity Index (CDAI), and Boolean remission responses). There were high numbers of responders in all ALX-0061 treatment groups, with DAS28 remission observed in 63% of ALX-0061-treated subjects at Week 24, and none of the ALX-0061-treated subjects showed worsening of disease activity during the study period. Overall, the efficacy profile obtained at Week 12 continued to improve during the subsequent 12 weeks of ALX-0061 treatment.

Pharmacokinetics

The pharmacokinetics of ALX-0061 appear dose-dependent, suggesting target-mediated disposition of the drug. A 2-compartment disposition model with parallel first-order (linear total body clearance [CL]) and Michaelis-Menten elimination (nonlinear or concentration-dependent CL) describes well the PK behavior of the drug, and is consistent with the more than proportional increase of exposure and half-life of the drug with the increase of the dose. Similar to monoclonal antibodies, the Nanobody has a limited volume of distribution, corresponding to the plasma volume. As the PK of ALX-0061 is dose-dependent due to a different contribution of the non-linear clearance at different serum concentrations, also the terminal half-life ($t_{1/2}$) is dose-dependent. At high concentrations, when non-linear clearance becomes negligible, the apparent $t_{1/2}$ estimated from the linear clearance term only, is estimated at approximately 15 days.

Pharmacodynamics

- All ALX-0061 groups received biologically effective doses: rapid and long-lasting increases in IL-6 and sIL-6R concentrations were observed across all ALX-0061 dose groups. The PD results confirmed that sIL-6R (and IL-6) concentrations can be used as a biomarker for target engagement by ALX-0061.

- Dosing q4w at 3 mg/kg yielded the highest exposure, as indicated by the observed average trough levels (~ 10 µg/mL), strongest biomarker response (based on sIL-6R profile), and the highest clinical remission rates.

Safety

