Safety and tolerability assessments will include evaluation of AEs (including serious adverse events, infections, injection site and hypersensitivity reactions), laboratory assessment, urinalysis, vital signs, and physical examination.

Additional planned assessments include determination of ALX-0061 levels in serum. To assess immunogenicity, the presence of ADA will be measured in serum until the Follow-up Visit, with potentially further characterization by modified ADA (mADA) and neutralizing antibody (nAb) assay.

The anticipated study duration for each subject is a maximum of 114 weeks after entry into the OLE. Subjects who received study drug up to and including Week 102, should return for the End of Treatment Visit at Week 104, and for the Follow-up Visit 12 weeks after the last study drug administration at Week 102. The end of the study is defined as the time of the last visit of the last subject participating in the study.

Study Treatment Allocation

At the Week 24 (ALX0061-C201) or Week 12 (ALX0061-C202) visit of the previous study, informed consent will be obtained from all subjects who are deemed potentially eligible for the OLE study, according to the protocol-specified inclusion and exclusion criteria.

Eligible subjects will receive ALX-0061 150 mg s.c. injections beginning at Week 0 of the OLE and q2w thereafter up to and including Week 102.

At the study visits at Weeks 0, 4, 8, 12, 24, 36, 48, 60, 72, 84 and 96, study drug is to be administered s.c. at the study site. At all other time points, subjects are allowed to self-administer away from the clinic. Subjects unable to have injections administered away from the study site will be required to return to the site every 2 weeks for administration of study drug by an authorized health professional.

ALX-0061 will be supplied as a sterile liquid for s.c. injection at a volume of 1.0 mL in prefilled single-use syringes. More details (including information on drug accountability) are provided in section [3.3](#).

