3.2.2. EXCLUSION CRITERIA

Subjects meeting any of the following criteria may not be enrolled in the study:

1. Received TCZ during the preceding Study ALX0061-C202.
2. Received any prohibited treatment during the preceding Phase IIb studies (ALX0061-C201 or ALX0061-C202).
3. Diagnosis of or suspicion of a serious infection (requiring parenteral antibiotics and/or hospitalization) or TB during the preceding study.
4. Diagnosis of malignancy or demyelinating disease during the preceding study.

5. Any active or recurrent viral infection that based on the Investigator's clinical assessment make the subject unsuitable for the study, including recurrent/disseminated herpes zoster.
6. Diagnosis of congestive heart failure (CHF) class III or IV as defined by the New York Heart Association, unstable angina pectoris, myocardial infarction, cerebrovascular accident during the preceding study.
7. Planned donation of germ cells, blood, organs, or bone marrow during the course of the study or within 6 months thereafter.
8. Male with female partner who is planning to become pregnant within 6 months after last dosing.
9. Pregnant woman or female subjects who are breastfeeding.
10. History of anaphylactic reaction or serious hypersensitivity reaction during the previous study.
11. Anticipation that a live attenuated vaccine will be required during the study or within 6 months after last dosing.
12. Abnormality in laboratory test results observed at the Week 22 Visit for subjects participating in the preceding Phase IIb ALX0061-C201 study, or observed at the Week 10 Visit for subjects participating in the preceding Phase IIb ALX0061-C202 study:
 - a. ALT and/or AST levels \geq 2 times the ULN.
 - b. Hemoglobin levels \leq 85 g/L (8.5 g/dL).
 - c. Platelet count \leq $75 \times 10^9/L$ (75,000 cells/mm³).
 - d. Absolute neutrophil count: $< 1.5 \times 10^9/L$.
 - e. Serum creatinine levels \geq 1.5 mg/dL (133 μ mol/L).
 - f. Any other clinically significant abnormal laboratory result as evaluated by the Investigator.
 - g. If no laboratory test results of the Week 22 Visit (for subjects participating in the preceding ALX0061-C201 study) or the Week 10 Visit (for subjects participating in the preceding ALX0061 C202 study) are available, then laboratory values of tests performed between Week 22 and 24 (for study ALX0061-C201) or Week 10 and 12 (for study ALX0061-C202) will be taken into account for the exclusion criteria 12a to 12e listed above.

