- If a subject misses a self-administration time point a new injection should be performed as soon as the patient remembers and within 1 week of the planned missed self-administration time point. If later than 1 week of the missed self-administration time point, then the CRO should be contacted. In case of rescheduling of missed visits, the total duration of the assessment period should remain 104 weeks.

If a subject misses a dose of MTX on their regularly scheduled dosing date, they should take the forgotten dose as soon as they remember; however, if more than 72 hours have elapsed since the missed dose, the subject should contact the Investigator for further dosing instructions.

For all subjects, injections should not occur less than 1 week apart. The CRO/Sponsor should be contacted if this cannot be respected. In case of interruption of more than 2 consecutive administrations, the subject should be discontinued from the study.

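### The live-vaccine ban in section 3.3.5 normally ends about 2 weeks after the last dose, although exclusion criterion 11 uses a 6-month window; the roughly 10 weeks to the Follow-up Visit matter most

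*Protocol*

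**What the plan says.** Section 3.3.5 of the protocol, under Prohibited Medication, opens with "The following medications are prohibited during the study (up to and including Week 104 or Early Termination Visit". One of the bullets beneath it is "Use of any live attenuated vaccine". The vaccine item therefore takes its end date from the shared header.

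Exclusion criterion 11 in section 3.2.2 looks further ahead and bars a subject for "Anticipation that a live attenuated vaccine will be required during the study or within 6 months after last dosing".

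Four timing rules fix when the ban ends:

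- Section 3.1.1 places the last dose at Week 102 and the End of Treatment Visit at Week 104, and has subjects return "for the Follow-up Visit 12 weeks after the last study drug administration at Week 102".
- Section 3.2.3.2 plans the Early Termination Visit two weeks after the last dose for subjects stopping for non-efficacy reasons, "unless they discontinue during a study visit, in which case that becomes their Early Termination Visit". For efficacy discontinuations it is the visit at which the criteria are met.
- Section 3.4.1.2 says that after a missed self-injection "a new injection should be performed as soon as the patient remembers and within 1 week of the planned missed self-administration time point", while "the total duration of the assessment period should remain 104 weeks".
- Footnote D of the Schedule of Assessments allows 3 days either side of each post-baseline visit.

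The contraception rules in section 3.3.5 run to at least six months after the last dose, the same window as the matching entry criterion in section 3.2.1.

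**The concern.** The protocol applies two windows to the same hazard. At entry, a live vaccine is judged unsuitable until six months after the last dose. On study, the written restriction stops at Week 104 or Early Termination. A header that suits DMARDs, corticosteroids and opioids has been applied to an item whose risk follows residual drug effect, not the efficacy assessment period.

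A site that follows section 3.3.5 literally finds no bar to a live vaccine about one half-life after the last dose of an immunomodulator, in a subject who still has a study visit to come. Section 1.2.5 names infection as a reported risk of IL-6 pathway inhibition; it also says that no serious infections had been reported for ALX-0061. What is at stake is the safety of a subject with an unforeseen need for a live vaccine. No estimate or analysis depends on it.

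**Working it through.** **The plan's own figure.** Last dose at Week 102 plus 12 weeks gives Week 114, which agrees with the stated maximum study duration of 114 weeks.

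**Nominal gaps.**

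- Last dose to end of ban: 104 − 102 = 2 weeks (14 days).
- End of ban to Follow-up Visit: 114 − 104 = 10 weeks (70 days).
- End of ban to six months, taken as 26 weeks (182 days): 102 + 26 − 104 = 24 weeks (168 days).
- Follow-up Visit to six months: 182 − 84 = 98 days (14 weeks).

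**Other cases the protocol allows.** The Follow-up Visit is held at 84 days after the actual last dose. The gaps are 84 − t and 182 − t, where t is the number of days from the last dose to the end of the ban.

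| Case | t | Days to Follow-up | Days to 6 months |
|---|---|---|---|
| Nominal | 14 | 70 | 168 |
| Week 104 visit ±3 days | 11 to 17 | 67 to 73 | 165 to 171 |
| Week 102 dose 7 days late, visit ±3 days | 4 to 10 | 74 to 80 | 172 to 178 |
| Dosed, then discontinued at the same visit | 0 | 84 | 182 |
| Last dose 28 to 42 days before Early Termination (doses missed) | 28 to 42 | 42 to 56 | 140 to 154 |

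The same-day case is an edge case. It could arise if a subject is dosed on site, reacts during the 60-minute observation in section 3.3.4, and discontinues at that visit. Efficacy failures would be identified before dosing, because study drug is given after all other assessments (section 3.4.7).

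**Residual drug.** Section 1.2.4.1 gives a terminal half-life, "estimated from the linear clearance term only, is estimated at approximately 15 days". With first-order decay, the fraction of the level just after the last dose that remains at day d is 2^(−d/h), for half-life h. The 10-day row is an assumption to show the range.

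| Half-life | Day 14 | Day 21 | Day 84 | Day 182 |
|---|---|---|---|---|
| 15 days | 52.4% | 37.9% | 2.06% | 0.022% |
| 10 days (assumed) | 37.9% | 23.3% | 0.30% | below 0.001% |

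At 15 days, day 14 is 14/15 = 0.93 half-lives, day 84 is 5.6 and day 182 is 12.1.

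**Where the remaining exposure falls.** The share of exposure between days 14 and 182 that comes before day 84 is (f(14) − f(84)) / (f(14) − f(182)), where f is the fraction above. At 15 days this is (0.5237 − 0.0206) / (0.5237 − 0.0002) = 0.96. It is 0.99 at an assumed 10 days and 0.92 at an assumed 19 days. The 10 weeks to the Follow-up Visit therefore carry nearly all of the drug-related concern. The last 14 weeks rest on the sponsor's own six-month window.

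**The case against.** The strongest reply is that the two rules do different jobs. Exclusion 11 is an entry criterion about anticipated need; section 3.3.5 restricts medication on study. They can differ without contradiction, and exclusion 11 already removes foreseeable need. Section 3.3.5 also requires consultation with the Investigator before other medication is prescribed, and that Investigator can read the six-month figure in exclusion 11. The consent form and Investigator's Brochure, which were not available, may cover the point.

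The pharmacology also has limits. The 15-day half-life holds where non-linear clearance is negligible, so the calculation overstates persistence as levels fall. No document ties a residual concentration to live-vaccine risk. On this reasoning an extension to the Follow-up Visit would be enough, since no study contact is scheduled after it.

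Much of this stands, and it keeps the severity low. This is a mismatch of windows, not a clash between two on-study rules. But exclusion 11 is applied about two years before a completer's last dose and cannot cover need that arises later. Consultation supplies no post-dose limit, and the nearest written limit has already expired. The words *during the study* might be read to include follow-up, but the bracketed end date overrides that reading. Faster clearance at low levels only shifts more of the concern into the first 10 weeks. As for the length of the extension, six months is the sponsor's own window and the one section 3.3.5 already uses for contraception.

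**Conclusion.** The concern holds, at low severity. As written, the live-vaccine prohibition ends normally 2 weeks after the last dose. That is about 10 weeks before the Follow-up Visit and about 24 weeks short of the window in exclusion 11. What is left uncovered is an unanticipated live vaccine, for which the Investigator has no written post-dose limit.

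The conclusion rests on six months being 182 days, on first-order decay that ignores subcutaneous absorption, and on the protocol wording alone. The planned maximum of about 501 is an enrolment figure, not a count of subjects likely to need a live vaccine; the documents give no vaccination frequency. No endpoint, population or analysis is affected.

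**What to change.** Give the vaccine bullet its own end date: "Use of any live attenuated vaccine", followed by *from Week 0 until at least six months after the final injection*. Leave the other prohibited medications at Week 104 or Early Termination. Remind subjects of the restriction at the Follow-up Visit; section 3.4.1 already has medications recorded up to the last visit.

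The drafting cost is one bullet, with no new visit, procedure or data collection. If the change counts as a substantial amendment, section 4.1 requires ethics approval and, where local rules require it, competent authority approval, in the 12 countries listed in SAP section 5.3. Including it in the next amendment made for other reasons would limit that burden.
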